4.1 PRE-SCREENING PERIOD

4.1.1. Pre-Screening Visit

Sites are required to pre-screen subjects for study inclusion, evaluating CCR5 positive status by Immunohistochemistry (IHC) assay prior to performing a full screening visit. This assay will be performed in archival tissue from previous biopsy specimens. If archival tissue is not available then, fresh core or excisional biopsy will be obtained.

The subject will sign and date the pre-screening informed consent form (ICF) in-person or remotely prior to any study-related pre-screening procedures. The remote consenting will involve the site sending the pre-screening ICF to subject (via hard copy or email) to discuss the consent over the phone. The written informed consent must be signed and personally dated by the subject, sent back to the site and will then be signed by the person who conducted the informed consent discussion. The consent process and discussion over the phone will be captured in the medical records.

A unique identification number will be assigned to each subject who has provided written pre-screening informed consent. The subject unique identification number will incorporate a three-digit Study Center number (901, 902 or 903....) and a three-digit numeric ID assigned in successive order of entering the study after signing the pre-screening ICF at each center, beginning with 001 at each site (e.g. 901-001 or 902-001).

Subject Screening # :

XXX - YYY

XXX=Study Center

YYY=Subject Numeric ID

Once the pre-screening ICF has been signed, the following procedures and information will be obtained to confirm pre- eligibility including:

- Review of prior medical records
- CCR5+ status confirmed by archival or fresh biopsy from primary or metastatic site

A pre-screening log will be maintained to capture the following information:

- Subject unique identification number
- Patient initials
- Date pre-screened
- Initial eligibility
- Date of re-consent (for the full consent form) or reason for ineligibility

4.2 SCREENING PERIOD

4.2.1. Screening Visit (SV)

The subject (or Legally Acceptable Representative (LAR)) will sign and date the informed consent form (ICF) and Health Insurance Portability Accountability Act (HIPAA) authorization (according to site policy and practices) prior to any study-related procedures. All study centers will be instructed to maintain the study-specific screening and enrollment logs at their sites. If a subject initially fails to meet inclusion/exclusion criteria and is later reconsidered for participation, the subject will be re-consented and assigned a new unique identification number at the time of re-screening. Subjects who fail their first screening attempt may be re-screened a maximum of once and may be enrolled if they are found to meet all inclusion and no exclusion criteria when re-screened.

Once the Screening ICF has been signed, screening procedures and information will be obtained to confirm subject eligibility including:

- Demographic information and baseline disease characteristics (see [Section 7.3](#)),
- Medical history (see [Section 7.4](#)),
- Prior medications assessment (see [Section 7.5](#)),
- Vital Signs (see [Section 7.6](#)),
- Body Weight & Height measurements (see [Section 7.6](#)),
- Physical examination (see [Section 7.7](#)),
- Eastern Cooperative Oncology Group (ECOG) Performance Review (see [Section 7.8](#))
- 12-lead Electrocardiogram (see [Section 7.9](#))
- Tumor imaging assessment (see [Section 7.15](#))

Note: Prior imaging assessment within the last 3 months of the Screening Visit is acceptable

- Collection of lab specimens (see [Section 7.11](#)) for
 - Complete blood count
 - Biochemistry
 - Serum pregnancy test, for female subjects of childbearing potential.
 - Urine sample for urinalysis parameters

All screening information will be fully documented in the subject's medical records (i.e., source documents).

- For consented subjects who do not meet eligibility criteria, a Screen Failure Case Report Form (CRF) will be completed. The Screen Failure CRF will contain the following details: the subject identification number, the date of ICF signature, demographic information (see [Section 7.3](#)), and the reason for screen failure. No additional information will be required for subjects who fail screening.
- For consented subjects who meet eligibility criteria, all required screening information will be transcribed onto the appropriate page of the CRF.

4.3 TREATMENT PERIOD

Subjects who meet all eligibility criteria, as per data gathered from Screening Period are to be treated. All subjects who fail to meet eligibility criteria will be considered screen failure and exit the study without further evaluation

The maximum sample size for this study is 30 subjects that will be followed by treatment according to the schedule described above starting at Treatment Visit 1 (Week 1).

Treatment may continue until one of the following criteria applies:

- Disease progression,
- Intercurrent illness that prevents further administration of treatment,
- Unacceptable adverse event(s), or
- Withdrawal of consent

4.3.1. Treatment Period, T1 (Week 1)

The following assessments will be performed at the first treatment visit of the treatment period:

- Concomitant medications assessment (see [Section 7.5](#)),
- Vital Signs and body weight measurement (see [Section 7.6](#)),
- Physical examination, including evaluation of all body systems (see [Section 7.7](#))
- ECOG Performance Status (see [Section 7.8](#))
- 12-lead Electrocardiogram (see [Section 7.9](#))
- Collection of lab specimens (see [Section 7.11](#)) for
 - Complete blood count

- Biochemistry
- Urine pregnancy test, for female subjects of childbearing potential.
- Urine sample for urinalysis parameters
- CTC and CAML analysis

Note: Complete blood count, biochemistry and urinalysis can be performed within 3 days prior to each visit.

- Leronlimab (PRO 140) Administration (see [Section 6.1.3](#))
- Post Injection Site Evaluation (performed by Investigator) (see [Section 7.13](#))
- Toxicity assessment (see [Section 7.10](#)) and Review of Adverse Events (see [Section 9](#))
- Standard-of-care chemotherapy (see [Section 7.17](#))

4.3.2. Treatment Period, T2 (Week 2) Onward

The following assessments will be performed at during the remaining visits during the treatment period:

- Concomitant medications assessment (see [Section 7.5](#)),
- Vital Signs (see [Section 7.6](#)),
- Body weight measurement on T4, T7, T10, and every 3 weeks after (see [Section 7.6](#)),
- Physical examination, including evaluation of all body systems on T4, T7, T10, and every 3 weeks after (see [Section 7.7](#))
- ECOG Performance Status on T4, T7, T10, and every 3 weeks after (see [Section 7.8](#))
- Collection of lab specimens (see [Section 7.11](#)) on T4, T7, T10, and every 3 weeks after for
 - Complete blood count
 - Biochemistry
 - Urine pregnancy test, for female subjects of childbearing potential
 - Urine sample for urinalysis parameters
 - CTC and CAML analysis

Note: Complete blood count, biochemistry and urinalysis can be performed within 3 days prior to each visit.

- Leronlimab (PRO 140) Administration (see [Section 6.1.3](#))
- Post Injection Site Evaluation (performed by Investigator) (see [Section 7.13](#))
- Toxicity assessment (see [Section 7.10](#)) and Review of Adverse Events (see [Section 9](#))
- Standard-of-care chemotherapy (See [Section 7.17](#))
- Tumor imaging assessments every 3 months or according to institution's standard practice

Subjects will be allowed to continue treatment until any one of the following occurs: progressive disease or unacceptable toxicity or withdrawal of consent.

4.4 FOLLOW-UP PERIOD

Duration of Follow Up

- An End of Treatment (EOT) visit will be conducted 30 (\pm 3) days after the last treatment visit (i.e., after last dose of leronlimab (PRO 140)).
- All patients will be followed for adverse events for 30 days after last dose of leronlimab (PRO 140) or until the patient starts a new treatment, whichever occurs first.
- Subjects who discontinue treatment for unacceptable adverse event(s) will be followed until resolution or stabilization of the adverse event (i.e. the grade is not changing).
- If a subject stops treatment due to unacceptable adverse event(s) but has not demonstrated disease progression, then the subject will be followed with imaging studies every 9 weeks until the time of progression radiographically according to RECIST v1.1 criteria. In the event that a radiographic response is detected, then this event will be included as a response in the final analysis, and the time of progression used in calculation of the survival analysis.
- Subjects will be followed up by clinic visits or phone call or another method of contact, for survival status every 3 months (\pm 1 month) for 2 years after treatment discontinuation or until death, whichever occurs first.

4.4.1. End of Treatment Visit (EOT)

An EOT visit will take place 30 (\pm 3) days from the last treatment visit.

The following assessments will be performed at the EOT visit:

- Concomitant medications assessment (see [Section 7.5](#)),
- Review of Adverse Events (see [Section 9](#))

- Vital Signs (see [Section 7.6](#)),
- Physical examination, including evaluation of all body systems (see [Section 7.7](#)),
- ECOG Performance Status (see [Section 7.8](#)),
- 12-lead Electrocardiogram (see [Section 7.9](#)),
- Toxicity Assessment (see [Section 7.10](#)),
- Collection of lab specimens (see [Section 7.11](#)) for
 - Complete blood count
 - Biochemistry
 - Urine sample for urinalysis parameters
 - CTC and CAML Analysis
- Survival status (see [Section 7.16](#))

4.4.2. Survival Follow-up Visits

Survival follow-up visits will be performed every 3 months (± 1 month) for 2 years after treatment discontinuation or until death, whichever occurs first. Subjects will be followed up by clinic visits or phone call or another method of contact, for survival status. During the visit, the following assessments will be performed:

- Survival status
- Concomitant medications (limited to all subsequent anti-cancer treatments)
- Toxicity assessment

***Note:** Subjects who discontinue treatment for unacceptable adverse event(s) will be followed until resolution or stabilization of the adverse event (i.e. the grade is not changing).*

- Tumor imaging assessment (see [Section 7.15](#) and note below)

***Note:** If a subject stops treatment due to unacceptable adverse event(s) but has not demonstrated disease progression, then the subject will be followed with imaging studies every 9 weeks until the time of progression radiographically according to RECIST v1.1 criteria. In the event that a radiographic response is detected, then this event will be included as a response in the final analysis, and the time of progression used in calculation of the survival analysis.*

4.5 UNSCHEDULED VISITS

In the event that the subject will return to clinic at a time other than a regularly scheduled study visit, the visit will be regarded as an unscheduled visit. Assessments at unscheduled visits are at the discretion of the Investigator. All pertinent findings, including adverse events or changes in medications, will be noted in the eCRF.

Any hospitalization or ER visits in between the scheduled visits should be promptly notified to the site staff.

5 SUBJECT COMPLETION, WITHDRAWAL AND CRITERIA FOR STOPPING THE STUDY

A subject is considered to have completed the study once all survival follow-up visit assessments up to 2 years after treatment discontinuation have been performed or until death, whichever occurs first.

While subjects are encouraged to complete all study evaluations, they may withdraw from the study at any time and for any reason. Reasonable effort will be made to determine why any subject withdraws from the study prematurely. This information will be recorded. If a subject withdraws prematurely after dosing, subjects will be monitored until they are stable for discharge from the clinic. All data normally collected at the scheduled Post-Study (Follow-up) Visit should be recorded at the time of premature discontinuation.

5.1 REMOVAL OF SUBJECTS FROM STUDY TREATMENT AND/OR STUDY AS A WHOLE

Subjects can be taken off the study treatment and/or study as a whole at any time at their own request, or they may be withdrawn at the discretion of the investigator for safety, behavioral or administrative reasons. The reason(s) for discontinuation must be clearly documented on the appropriate eCRF and may include:

- Subject voluntarily withdraws from treatment (follow-up permitted)
- Subject withdraws consent (no follow-up permitted)
- Subject is unable to comply with protocol requirements
- Subject demonstrates disease progression
- Subject experiences unacceptable toxicity
- Treating physician determines that continuation on the study would not be in the subject's best interest
- Subject becomes pregnant
- Subject develops a second malignancy that requires treatment which would interfere with this study
- Subject becomes lost to follow-up (LTf)

If a subject fails to return for the scheduled study visit or is discontinued from the study, an attempt will be made to determine the reason(s). If the subject is unreachable by telephone, a registered letter will be sent to the subject requesting that he/she contact the clinic.

All patients with an ongoing SAE at the Post-Study (Follow-up) Visit (scheduled or premature) must be followed until the event is resolved (with or without sequelae) or deemed stable.

5.2 DATA COLLECTED FROM WITHDRAWN SUBJECTS

Every attempt should be made to collect follow-up information. The reason for withdrawal from the study will be recorded in the source documents and on the appropriate page of the CRF.

Before a subject is identified as lost-to-follow up, the site should make all reasonable efforts to contact the subject. These attempts must be documented and should include at a minimum one phone call and one certified letter.

In the event that a subject is withdrawn from the study at any time due to an adverse event or SAE, the procedures stated in [Sections 9.2](#) and [9.4](#) must be followed.

5.3 SCREEN FAILURES

A subject who signed a consent form, but did not meet the inclusion/exclusion criteria is classified as a screen failure. Subject number, demographics and reason for screen failure will be recorded.

In the event that a subject initially fails to meet inclusion/exclusion criteria and is later reconsidered for participation, will be re-consented and assigned a new screening number at the time of re-screening. Subjects who fail their first screening attempt may be re-screened again (i.e., up to two screenings) and may be enrolled if they are found to meet all inclusion and no exclusion criteria at the subsequent screening visit.

6 STUDY TREATMENT

Eligible subjects will receive leronlimab (PRO 140) administered weekly at a dose of 525 mg SC until disease progression or intolerable toxicity.

Table 6-1: Treatment Administration Summary

Study Drug	Premedication	Dose	Route	Schedule	Supportive Therapies
Leronlimab (PRO 140)	N/A	525 mg	SC	Start on Week 1 and every week thereafter	N/A

Supportive care: Any required supportive care treatment such as antibiotics, anti- emetics, proton pump inhibitors and others will be given per institutional standards.

6.1 LERONLIMAB (PRO 140)

Leronlimab (PRO 140) is a humanized IgG4,κ monoclonal antibody (mAb) to the chemokine receptor CCR5. Leronlimab (PRO 140) is provided at a concentration of 175 mg/mL and is intended for SC route of administration.

Each vial of the leronlimab (PRO 140) product contains ~2.4 mL antibody at 175mg/mL in a buffer containing 5 mM L-histidine, 15.0 mM glycine, 95 mM sodium chloride, 0.3% (w/v) sorbitol, 0.005% (w/v) polysorbate 20 (Tween 20®), and sterile water for injection, at pH of 5.5.

Note: *1.5 mL will be drawn from 2.4 mL solution in a vial. Remaining 0.9 mL medication will be discarded appropriately from each vial.*

A total 525 mg of leronlimab (PRO 140) (175 mg/mL) is delivered as

- two injections of 1.5 mL administered subcutaneously on opposite sides of the abdomen, or
- one injection of 3 mL administered subcutaneously on one side of the abdomen.

6.1.1. Leronlimab (PRO 140) - Packaging and Labeling

Study drug will be prepared by Ajinomoto Althea, Inc. and will be packaged, labeled, and shipped by PCI Pharma Services.

The contents of each vial are described in [Section 6.1](#). Leronlimab (PRO 140) kits will be labeled with information such as: study protocol #; fill volume; concentration; storage condition; a “use as per study protocol” statement; a cautionary statement; sponsor’s name and address; and the kit number.

Below are representative samples of the Investigational Product, FDP individual vial (Figure 6-1), syringe label (Figure 6-2), and kit labels (Figure 6-3) designated for use in this clinical protocol. Each kit contains two labeled vials and two syringe labels.

Figure 6-1: Investigational Product - Vial Label

Protocol: CD09_Basket	Kit No. xx	Protocol: CD09_Basket	Kit No. xx
Subject No. _____		Subject No. _____	
Single use 3 mL vial contains 2.4 mL of PRO 140 (175 mg/mL) solution for subcutaneous injection		Single use 3 mL vial contains 2.4 mL of PRO 140 (175 mg/mL) solution for subcutaneous injection	
Store at 2°C to 8°C (36°F to 46°F)		Store at 2°C to 8°C (36°F to 46°F)	
USE AS PER STUDY PROTOCOL		USE AS PER STUDY PROTOCOL	
Caution: New Drug – Limited by Federal (or United States) Law to Investigational Use		Caution: New Drug – Limited by Federal (or United States) Law to Investigational Use	
CytoDyn Inc., Vancouver, WA, USA		CytoDyn Inc., Vancouver, WA, USA	

Figure 6-2: Investigational Product - Syringe Label

Protocol: CD09_Basket	Contents of Kit No. xxx
This syringe contains 1 mL, 1.5 mL, 2mL or 3 mL PRO 140 (175 mg/mL) solution for subcutaneous injection	
USE AS PER STUDY PROTOCOL	
Caution: New Drug – Limited by Federal (or United States) Law to Investigational Use	
CytoDyn Inc., Vancouver, WA, USA	

Figure 6-3: Investigational Product - Kit Label

Protocol: CD09_Basket	Kit No. xxx
Site No. _____	Subject No. _____
This kit contains XX single-use vials	
Each 3 mL vial contains 2.4 mL of PRO 140 (175 mg/mL) solution for subcutaneous injection	
Store at 2°C to 8°C (36°F to 46°F)	
USE AS PER STUDY PROTOCOL	
Caution: New Drug – Limited by Federal (or United States) Law to Investigational Use	
CytoDyn Inc., Vancouver, WA, USA	

The pharmacy manual provides the criteria regarding vial acceptance or rejection, as well as instructions for the preparation of the IP syringes to be used to administer drug.

6.1.2. Leronlimab (PRO 140) - Storage and Handling

Study drug will be shipped at 2°C to 8°C (refrigerated [36°F to 46°F]) to the investigator's site. Upon receipt at the site, the responsible site staff or pharmacist should verify the integrity of the vials. Study drug should be stored at 2°C to 8°C (refrigerated [36°F to 46°F]). The contents of the vial should appear as a clear to opalescent, colorless to yellow solution; fine translucent particles may be present. This is normal.

The investigator must maintain an accurate record of the shipment, storage, and dispensing of the study drug in a drug accountability log. An accurate record including the date and amount of study drug dispensed to each subject must be available for inspection at any time. A study CRA assigned to monitor the investigational site will review these documents once study drug has been received by the investigational site. Study drug will be accounted for on an ongoing basis during the study.

6.1.3. Leronlimab (PRO 140) - Administration

Guidelines for dose preparation can be found in the pharmacy manual.

Leronlimab (PRO 140) will be provided to the administering personnel in single-use syringes prepared from vials of study drug stored at 2-8°C at the site pharmacy prior to use.

A 25-gauge needle will be used for Leronlimab (PRO 140) administration. PRO 140 should be administered slowly over 15 seconds per mL. The IP should not be kept in syringe for longer than 60 minutes.

Following each SC delivery of drug, careful examination will be made to assess the appearance of any study drug Injection Site Reactions (ISRs) as per CTCAE v5.0

All doses of study drug will be prepared by either the credentialed pharmacist or qualified medical professional and will be administered as SC injection by a licensed medical professional when leronlimab (PRO 140) is administered at clinic site. Self administration by subjects at home is allowed at certain visits.

All initial leronlimab (PRO 140) SC weekly injections must be administered at clinic. The remaining study treatment injections may be self-administered by subjects at home after proper training by a healthcare professional.

Note: It is preferred that the same injection site be used throughout the study. At the same time, it is not recommended to inject the study drug into areas where skin shows signs of a previous injection site reaction. It is advised to change the injection site if any previous injection site reaction remains unresolved.

6.1.4. Leronlimab (PRO 140) - Post Injection Monitoring

Subject will be observed at approximately 30 minutes post-injection or longer if necessary for injection site reaction as per CTCAE v5.0.

In addition, the tolerability of repeated subcutaneous administration of leronlimab (PRO 140) is evaluated based on assessment of subject-perceived injection site pain using the Pain Visual Analog Scale (VAS).

6.1.5. Leronlimab (PRO 140) - Dose Modifications

The dose interruption and permanent discontinuation for any toxicity are described below.

Dose interruption: Refer to [Table 6-2](#) below. Recovery to acceptable levels must occur to allow leronlimab (PRO 140) continuation. Any adverse event deemed to be related to leronlimab (PRO 140) that requires a dose hold of more than 21 days will result in permanent discontinuation of leronlimab (PRO 140).

Table 6-2: Leronlimab (PRO 140) Dose Modification and Management for Injection Site Reactions

CTCAE Grade	Treatment Modifications
Grade 1	No dose adjustment is required.

Grade 2	First Occurrence: No dose adjustment is required. Second Occurrence of the same event: Closely follow-up for resolution of the AE to Grade ≤ 1
Grade 3	Withhold treatment until symptoms resolve to: • Grade 1 or less
Grade 4	Study treatment will be permanently discontinued

Permanent discontinuation of Treatment: If toxicity is reported at 525mg dose.

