9.2.6. Injection-site reactions

Injection-site reactions thought to be directly related to the injection are considered to be AEs of special interest, and will be assessed as per CTCAE v5.0.

For subjects who develop Grade 1 or Grade 2 events, therapy will be continued as per protocol. If a subject chooses to discontinue study treatment, the site should notify the protocol team leadership, and encourage the subject to complete any remaining study visits until the toxicity resolves.

For subjects who develop Grade 3 events following study drug injection, the subject should be reevaluated closely until the AE returns to Grade 1 or less, at which time study treatment may be reintroduced at the discretion of the site investigator. If the same Grade 3 AE recurs following the next administration of study drug, study treatment must be permanently discontinued. Subjects experiencing Grade 3 AEs requiring permanent discontinuation of study treatment should be followed closely for resolution of the AE to Grade 1 or less and the team leadership must be notified.

For Grade 4 events permanently discontinue therapy.

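### Section 6.1.5 ends by ordering a permanent stop for any toxicity at 525 mg, which contradicts the graded injection-site rules and the protocol's general stopping criterion

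*Protocol*

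**What the plan says.** Section 6.1.5 of the protocol announces its scope broadly: "The dose interruption and permanent discontinuation for any toxicity are described below". It then gives three things.

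- **A hold rule.** "Recovery to acceptable levels must occur to allow leronlimab (PRO 140) continuation", and "Any adverse event deemed to be related to leronlimab (PRO 140) that requires a dose hold of more than 21 days" ends treatment permanently.
- **Table 6-2, for injection-site reactions.** Grade 1 needs no adjustment. For Grade 2 the entry is "First Occurrence: No dose adjustment is required", with close follow-up at a second occurrence. For Grade 3 it is "Withhold treatment until symptoms resolve to" Grade 1 or less. Grade 4 is a permanent stop.
- **A closing line.** "Permanent discontinuation of Treatment: If toxicity is reported at 525mg dose".

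Section 9.2.6 covers injection-site reactions again. "For subjects who develop Grade 1 or Grade 2 events, therapy will be continued as per protocol". After a Grade 3 event the subject is followed until Grade 1 or less, "at which time study treatment may be reintroduced at the discretion of the site investigator". Recurrence of the same Grade 3 event at the next dose, or any Grade 4 event, is a permanent stop.

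The general criteria for ending treatment are unacceptable adverse events (4.3), unacceptable toxicity (4.3.2 and 5.1) and intolerable toxicity (6). Section 8.1 lists 525 mg as the only treatment group. Section 3 lets subjects enrolled under version 1.0 stay on 350 mg.

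**The concern.** The closing line is an operative dosing instruction, and it cannot be followed together with the rules around it. The word toxicity does not supply a threshold: section 8.7.3.1 treats toxicities and AEs as one category graded by CTCAE, which starts at mild, asymptomatic events.

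Three things are at stake.

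- **Subjects.** Patients with advanced cancer could be taken off drug for mild, tolerable events that the rest of the protocol treats through. The trigger is foreseeable: the background section reports injection-site reactions, mostly mild, in earlier leronlimab studies, although in other populations and at other doses.
- **Safety reporting.** SAP 8.3.1 plans a summary of adverse events leading to treatment discontinuation. If sites read the rule differently, those counts would partly reflect the reading and not tolerability, which is a secondary objective.
- **Deviations and the Per Protocol set.** Section 11.4.1 makes failure to withdraw a subject who met withdrawal criteria a major deviation, and SAP 8.1.2 has a matching category. Major violations remove subjects from the Per Protocol population. A site that follows Table 6-2 at Grade 1 could be held in breach of 6.1.5, and a site that follows 6.1.5 departs from Table 6-2 and 9.2.6.

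**Working it through.** The plan states no figure on this point and the check needs no statistical calculation. The rules are set side by side for a subject on 525 mg.

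| Event | Closing line of 6.1.5 | Table 6-2 | Section 9.2.6 |
|---|---|---|---|
| Injection-site reaction, Grade 1 | Stop | Continue | Continue |
| Injection-site reaction, Grade 2 | Stop | Continue; close follow-up if repeated | Continue |
| Injection-site reaction, first Grade 3 | Stop | Hold to Grade 1 or less | Hold; may resume |
| Injection-site reaction, same Grade 3 again | Stop | Hold to Grade 1 or less | Stop |
| Injection-site reaction, Grade 4 | Stop | Stop | Stop |

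**Count for Table 6-2.** It has four grade rows. Grades 1, 2 and 3 conflict with the line and Grade 4 agrees: 3 of 4 conflict.

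**Count for 9.2.6.** It gives four outcomes. Continuing at Grades 1–2 and possible reintroduction after a first Grade 3 conflict; the stops for recurrent Grade 3 and for Grade 4 agree: 2 of 4 conflict.

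**Other toxicities.** The line stops treatment at any grade and whatever the cause. Sections 4.3, 4.3.2, 5.1 and 6 stop it only when toxicity is judged unacceptable or intolerable. The two cannot both govern a mild, tolerable event.

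**The hold rule in the same section.** The recovery sentence and the 21-day limit both presuppose that dosing can be paused and resumed. If any reported toxicity ends treatment, there is no hold to recover from and none to time. For subjects on 525 mg the line makes both sentences redundant.

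**Reach of the line.** Since 525 mg is the assigned dose, the line covers everyone except version 1.0 subjects who stay on 350 mg. Those subjects fall outside its wording, so the literal rule is strict at one dose and absent at the other.

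**A second mismatch.** The fourth row shows that Table 6-2 and 9.2.6 also differ from each other: the table has no stop for a recurrent Grade 3 reaction.

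**The case against.** The best answer is that the line has simply lost an adjective. The protocol gives a threshold many times: Section 6 itself opens by tying 525 mg weekly dosing to intolerable toxicity, and other sections use unacceptable. Section 7.10 also points sites to Table 6-2 for managing any toxicity. The graded rules appear twice and agree that drug continues, or may resume, through a first Grade 3 reaction. An experienced investigator would probably follow them. The List of Tables numbers the injection-site table 6-3 while the body calls it 6-2, which is consistent with unfinished editing, though that is only an inference. The trial has one arm, up to 30 subjects and no formal hypothesis test, and the safety summaries are descriptive.

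Much of this is fair. Limits do exist elsewhere; the fault is that the line neither repeats them nor refers to them. This looks more like a drafting failure than a deliberate zero-tolerance policy. The row counts measure conflicting text and not patients, and there is no evidence that any site has stopped drug for a Grade 1 event.

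None of it removes the clash. The limits stated elsewhere are the very rules the line contradicts. The cross-reference in 7.10 leads to a table that contradicts the line for injection-site reactions and gives no graded rule for anything else. A dosing instruction should not depend on sites disregarding its last sentence.

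**Conclusion.** The concern holds, and the line should be fixed. As written, the closing line of 6.1.5 is wrong: it conflicts with Grades 1 to 3 of Table 6-2, with two of the four outcomes in 9.2.6, and with the general stopping criterion for all other events. It agrees with the graded rules only where they already require a permanent stop.

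The practical consequences are conditional on how sites read it. The number of subjects affected cannot be estimated, because the documents give no toxicity rate for 525 mg weekly in patients with solid tumors. No effect on the primary PFS analysis is shown; section 8.7.3 includes everyone who received at least one dose. The likely effects are on exposure, on the table of discontinuations due to adverse events, and on the classification of major deviations that determines the Per Protocol set.

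The conclusion rests on reading the line as printed. The sponsor may have meant unacceptable toxicity, or that no dose reduction is offered, but the line says neither.

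**What to change.** Replace the closing line of 6.1.5 with the permanent-stop triggers the protocol already contains, applied at both 350 mg and 525 mg:

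- a Grade 4 injection-site reaction;
- recurrence of the same Grade 3 injection-site reaction at the next dose;
- a leronlimab-related adverse event that needs a hold of more than 21 days;
- toxicity that the investigator judges unacceptable.

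Add the recurrent Grade 3 stop to the Grade 3 row of Table 6-2 so that it matches 9.2.6. If the intent was that no dose reduction is available, say so in a separate sentence. The clinical thresholds are for the sponsor and investigators to settle.

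The cost is one protocol clarification, covering one line of text and one table row. It adds no procedures, visits or patients.
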